#### 8.2. Schedule of Assessments

Prior to performing any trial assessments that are not part of routine medical care for the subject, the Investigator will obtain written informed consent as described in Section 5.2.

#### a) Baseline Assessments

The following assessments and procedures should be performed within 28 days before inclusion, and when applicable, as close as possible to the start of study treatment:

- Informed consent
- Screening registration
- Inclusion /exclusion criteria
- Medical history including previous cancers treatments
- Histology confirmation of disease
- BRAF mutation status (local)
- Anamnesis
- Demographics
- Physical examination and vital signs
- ECOG performance status
- Neurologic examination and Modified Barthel Index
- Ophthalmologic anamnesis and evaluation by Oncologist (if there's any alarm symptom or sign, patient will be evaluated by Ophthalmologist)
- ECG
- Concomitant medications
- Quality of Life questionnaires (QoL)

- Haematology, coagulation, serum biochemistry including CK and LDH determination (within 72 h before).
- Urine pregnancy test for woman of childbearing potential (within 72 h before), and in case this test be positive, a serum pregnancy test should be done.
- LVEF
- CT Scan
- Contrast enhanced brain MRI
- Colour Digital Photography (including a metric ruler) of the skin lesions

# b) Prior treatment administration (≤7 days before day 1 (D1) of cycle 1 (C1)):

The following assessments and procedures should be performed within 7 days before start of study treatment (determination performed during "baseline assessments" can be used for the purposes of "prior treatment determination" if they are performed within 7 days before start of treatment):

- Physical examination and vital signs
- ECOG performance status
- SAEs related to study procedures (e.g. blood sampling) must be reported including screening failures (and reason for screening failure)
- Concomitant medications
- Urine pregnancy test for women of childbearing potential (within 72 h before) and in case this test be positive, a serum pregnancy test should be done
- Haematology, coagulation, serum biochemistry including CK and LDH determination (within 72 h before).

#### c) On treatment visits

#### 1. - On week 4

- Physical examination
- Vital signs
- ECOG performance status
- Neurologic examination and Modified Barthel Index
- Ophthalmologic anamnesis and evaluation by Oncologist (if there's any alarm symptom or sign, patient will be evaluated by Ophthalmologist)
- ECG
- Adverse events follow-up
- Concomitant medications
- Haematology, coagulation, serum biochemistry, pregnancy test (urine test, and in case this test be positive, a serum pregnancy test should be done to confirm no pregnancy).
- COMBO450 follow up and dispensing

# 2. - On week 8

- Physical examination
- Vital signs
- ECOG performance status
- Neurologic examination and Modified Barthel Index

- Ophthalmologic anamnesis and evaluation by Oncologist (if there's any alarm symptom or sign, patient will be evaluated by Ophthalmologist)
- Adverse events follow-up
- Concomitant medications
- Haematology, coagulation, serum biochemistry,
- CT Scan
- Contrast enhanced brain MRI
- Colour Digital Photography (including a metric ruler) of the skin lesions
- QoL

# 3. - Every 4 weeks until disease progression

- Physical examination
- Vital signs
- ECOG performance status
- Neurologic examination and Modified Barthel Index
- Ophthalmologic anamnesis and evaluation by Oncologist (if there's any alarm symptom or sign, patient will be evaluated by Ophthalmologist)
- Adverse events follow-up
- Concomitant medications
- Haematology, coagulation, serum biochemistry
- Pregnancy test ( urine test, and in case this test be positive, a serum pregnancy test should be done to confirm no pregnancy.)
- COMBO450 follow up and dispensing

# 4. - Every 8 weeks until disease progression

- CT Scan
- Contrast enhanced brain MRI
- Colour Digital Photography (including a metric ruler) of the skin lesions
- QoL (on week 24)

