- After progression, patients will be followed only for overall survival.
  - o In case of encorafenib and binimetinib are providing a clinical benefit to any patient, treatment could be continued after discussion with Sponsor if it agrees on that. In this case, follow up will be done as per institutional criteria. In the study, these patients will be followed only for overall survival.
- Study assessments: in each monthly visit, adverse events will be registered, blood samples will be collected for blood cell counts and general biochemistry (including magnesium, potassium and creatinine-kinases); an ECG will be performed at baseline, after one month of treatment, and every 3 months thereafter; a left ventricular ejection fraction (LVEF) evaluation will be performed by as per institutional guidelines at baseline and every 3 months thereafter ophthalmologic anamnesis and evaluation will be performed by oncologist at baseline and in every monthly visit, if there's any alarm symptom or sign, patient will be evaluated by Ophthalmologist. Body CT-scan and contrast enhanced brain MRI will be performed baseline and every 8 weeks up to 12 months and according to normal practise thereafter. More information regarding study determination is provided in section 8 of this protocol.

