# 8. STUDY ASSESSMENTS

# 8.1. Schedule for tests and determinations

Table 11. Schedule for tests and determinations

Visit	Baseline (D-28 to D-1)	w4	w8 (D-56)	Every 4w	Every 8w	Every 12 w	End of treatment (28 +/-4d)	FU before DP	FU after DP for OS
Informed consent	Х								
Screening registration	Х								
Histology confirmation of disease	Х								
BRAF Status	×								
Anamnesis	Х								
Demographics	Х								
Physical examination / vital signs	х	Х	х	Х			Х		
ECOG PS	×	Х	х	Х			X	Х	
Basic neurologic examination and Modified Barthel Index	Х	Х	X	Х			X	×	
Ophthalmologic anamnesis an evaluation by Oncologist	Х	X	X	Х			X		
Ophthalmologist exploration	If clinical suspicion								
ECG	×	Х				Х	×		
LVEF (as per institutional guidelines)	X					Х			
Concomitant medications	×	Х	Х	Х			Х		
Inclusion/exclusion criteria	×								
QoL	×	X at weeks 8 and 24							
Analytical tests									
Clinical laboratory test	×	Х	Х	Х			X	Х	
Pregnancy test	Х			Х			×		
Disease evaluation									
Abdominopelvic CT Scan (1)	Х		Х		X (³)			X (every 8w) (³)	
Brain MRI (  )	х		Х		X (³)			X (every 8w) (³)	

Colour Digital Photography (including a metric ruler) of skin lesions (¹)	х		Х		X (³)			X (every 8w) (³)	
Safety evaluation									
Adverse events and Serious Adverse events		Every 4 weeks throughout all the study (From ICF signature up to EoT visit)							
Study Treatment									
COMBO450 follow-up and dispensing		Х		х					
Dose reduction		Throughout all the study, when applicable							
Dose delay		Throughout all the study, when applicable							
Long term FU									
OS Follow-up									Х
New anti-cancer therapy									Х

 $(^1)$  Out of the assessments indicated by protocol, patients can be assessed whenever the investigator considers it indicated.

 Contrast enhanced MRI.

 $(^3)$  Assessments will be done every two months up to 12 months, thereafter, patients will be assessed as per institutional criteria.

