# **Protocol specifications for trial determinations**

**Informed Consent Form (ICF):** Determinations performed by routine clinical practice before signing the informed consent will be valid, provided they are carried out following from this protocol, if they have been performed during the period included in the table 11.

**Screening registration:** Any patient that sign ICF should be registered in the EDC system and have assigned a unique screening number.

**Anamnesis:** to be performed during the baseline period in the 2 weeks prior to inclusion. Medical history will include all active conditions and any condition diagnosed considered to be clinically significant by the investigator. Melanoma history will be recorded separately and not listed as Medical History.

**Demographics:** Date of birth, race, and sex.

**Physical examination/vital signs:** Complete physical examination, weight, height, and vital signs (pulse, respiratory rate, **blood pressure** and body temperature).

**ECOG-PS:** Functional status will be assessed using the ECOG score.

**Neurological examination:** Basic neurological assessment according to normal practice and Modified Barthel Index according to "Guidelines for the Modified Barthel Index of Activities of Daily Living"

**Ophthalmologic anamnesis and evaluation by Oncologist:** ophthalmologic anamnesis and evaluation performed by oncologist as a part of physical examination and it will be performed at baseline and in every monthly visit. Only if there's any alarm symptom or sign or previous ocular antecedents, patient will be evaluated by Ophthalmologist.

**Ophthalmologist examination:** Patient will be evaluated by Ophthalmologist if there's any alarm symptom or sign or previous ocular antecedents.

**ECG:** Standard 12-lead ECG at baseline, after 4 weeks of treatment, after every 12 weeks and in the end of treatment visit. Additional ECGs may be performed at the discretion of the investigator.

**Concomitant medication:** All drugs taken within 30 days before starting the trial and concomitantly during the study will be recorded in medical records and in eCRF with indication, dose information and administration dates.

**Inclusion and Exclusion Criteria:** Verification that patients meet all inclusion criteria and none of exclusion.

Quality of Life: EORTC QLQ 30 administered at baseline, at week 8 and week 24.

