#### Non-radiological Assessments

Visible cutaneous lesions must be measured clinically. Digital and standardized photographic images including a ruler for scale as part of the image are recommended for documentation. All clinical assessments must be performed within proximity (± 7 days) of any protocol specified radiographic assessments

**Safety evaluation:** Safety assessments and adverse events include tumour-related, unrelated and treatment-related signs and symptoms. Adverse events will be documented and recorded in the CRF upon patient notification. AEs will be collected from the signing of Informed Consent until the end of treatment visit (30 days after end of treatment) or up to resolution. Classification of toxicity will be done according to the common terminology criteria for adverse events of the National Cancer Institute, version 4.03 (NCI CTCAE v. 4.03).

**PFS follow-up:** Body CT-scan and contrast enhanced brain MRI will be performed baseline and every 8 weeks (+/-1 week) up to 12 months and according to normal practice thereafter **until disease progression**, **independently of the end of treatment reason if it was not the documentation of disease progression**.

**OS Follow-up:** After disease progression all patients will be monitored to determine subsequent antineoplastic treatments and survival. It is recommended to maintain contacts by phone or by other methods every 4 weeks to carry out timely follow-up (up to 24 months or study closure).

**New anti-cancer therapy:** Information on subsequent treatments should include the list of post-treatment treatments, the drugs administered, and the date of initiation and discontinuation of each drug. All data will be recorded in the medical record and in the eCRF.

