# e) Follow-up before progression disease

- ECOG performance status
- Neurologic examination and Modified Barthel Index
- Haematology, coagulation, serum biochemistry, and pregnancy test (urine test and in case this test be positive, a serum pregnancy test should be done to confirm no pregnancy.), (only if patient it's on treatment)
- CT Scan (every two months up to 12 months, thereafter patients will be assessed as per institutional criteria)
- Contrast enhanced brain MRI (every two months up to 12 months, thereafter patients will be assessed as per institutional criteria)
- Colour Digital Photography (including a metric ruler) of the skin lesions (every two months up to 12 months, thereafter patients will be assessed as per institutional criteria).

After one year of 1st day of treatment, follow up will be performed according local normal practise.

f) Follow-up before progression disease after ending treatment:

- Subjects who no longer receive study treatment due to progression should remain in follow-up until their death or until the closure of the study (whichever comes first).
- Subjects who no longer receive study treatment due to unacceptable toxicity or at the discretion of the investigator should remain in follow up until progression. Visits will be scheduled every 8 weeks and tumor evaluation should be performed every 8 weeks until tumor progression the fist year, and after 12 months, the tumor evaluation can be done as per institutional criteria. The tests and questionnaires can be done according to the normal practise too.
- Subjects who have switched to an alternative treatment do not perform a formal follow-up, except to record the date of the death.

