**Toxicity of the combination after local treatment:** Number of patients with adverse events and serious adverse events, changes in laboratory values, vital signs, electrocardiograms (ECGs), LVEF (MUGA (Multigated Acquisition Scan) / echocardiogram) and assessment of physician, dermatological and ocular examinations graded according to the National Cancer Institute (NCI) Common Terminology Criteria for Adverse Events (CTCAE) v 4.03 after local treatment (after end of local treatment date). It will be studied using descriptive statistics techniques, such as frequency tables and contingency tables. The final statistical analysis of this endpoint is expected to be performed within 6 months after database closure expected at 24 months after last patient inclusion, however interim analysis might be performed when analysing other primary variables.

**Quality of life:** Change from baseline in the global health status score of the EORTC QLQ-C30. The final statistical analysis of this endpoint is expected to be performed within 6 months after database closure expected at 24 months after last patient inclusion, however interim analysis might be performed when analysing other primary variables.

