#### 10.7. Statistical Methods

Analysis will be based on observed data, and missing data for dropouts are not replaced by methods like LOCF (last option carried forward).

Continuous data will be presented with the number of observations, mean value + standard deviation, median value + minimum and maximum. Categorical data will be presented as counts and percentages. Individual subject data will be listed.

Individual and summary vital signs, ECG parameters, clinical laboratory data (haematology, serum biochemistry and urinalysis) will be presented in tabular form. For the values outside the reference range will be flagged and for the clinically significantly abnormal values will be listed in tabular form. Adverse events will be tabulated by system organ class and preferred term after medical coding using the NCI CTCAE v 4.03.

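### The quality-of-life endpoint is defined for the whole of both cohorts, but its later form is collected only until progression, and the plan does not say that the result is limited in this way

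*Combined protocol and SAP*

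**What the plan says.** Quality of life in both cohorts is a secondary objective (protocol section 4.2). Section 10.2 defines it as "Change from baseline in the global health status score of the EORTC QLQ-C30". It gives no time point and no restriction to patients who are progression-free or on drug.

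The schedule appears in two forms:

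- **Section 8.1.** The text reads "EORTC QLQ 30 administered at baseline, at week 8 and week 24" and Table 11 reads "X at weeks 8 and 24". Neither attaches a condition.
- **Section 8.2 c), on-treatment visits.** The week-24 form is item 4's, and that item is headed "Every 8 weeks until disease progression".

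The other lists do not fill the gap. The end-of-treatment visit (8.2 d) and the follow-up before progression (8.2 e) contain no QLQ-C30. Section 8.2 f) covers patients who stopped drug for toxicity or by investigator decision. After a clause on tumour evaluation beyond 12 months, it adds: "The tests and questionnaires can be done according to the normal practise too". Section 5.3 states that "After progression, patients will be followed only for overall survival", and the synopsis says the same. Under 8.2 f), patients who switch to another treatment have only their date of death recorded.

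On analysis, section 10.7 uses observed data and says that "missing data for dropouts are not replaced by methods like LOCF". The SAP's QLQ-C30 tables, for cohort 2 (section 4.8 on) and in the separate quality-of-life report for all cohorts, have rows for baseline, w8 and w16. None has a row for week 24.

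**The concern.** The endpoint has no stated limit, but collection of the later form depends on an outcome. Progression is likely to go with worse quality of life, so week-24 forms will be missing for a reason linked to the value they would have recorded. An observed-data summary then describes the patients still being asked. A correctly paired change score does not cure this, because the comparison patients never received a form.

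What is at stake is interpretation. A reader of the results would take the figure as the cohort's quality of life about six months after starting treatment. Nothing in section 10.2 or the SAP warns otherwise, and nothing planned would show how many living patients were not asked.

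**Working it through.** **The plan's own figures.** The documents give no sample size or expected completion rate for quality of life. The only stated figure needed is the denominator, 48 + 15 = 63. The cohort 1 part reproduces under the normal approximation for response rates of 40% and 60%, one-sided 5%, power 80%:

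- n = ((1.645 × √(0.4 × 0.6) + 0.842 × √(0.6 × 0.4)) / 0.2)² = 37.1, rounded up to 38
- 38 / 0.8 = 47.5, rounded up to 48

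**Inputs for the illustration**

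- Median PFS 5.6 months: protocol section 3, from the cited trial of dabrafenib plus trametinib in brain metastases.
- Median PFS 11 months: same section, same combination in patients without brain metastases.
- Median OS 9 months: background figure in section 2.3. The upper value of 15 months is an assumption.
- Exponential curves: an assumption. The protocol states no PFS or OS expectation for this regimen.
- Times: week 16 = 16 × 7 / 30.4375 = 3.68 months; week 24 = 5.52 months.

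**Patients alive at week 24**

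- OS median 9: 0.5^(5.52/9) = 0.654
- OS median 15: 0.5^(5.52/15) = 0.775

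**Reading A: progression by week 24, including at that visit's scan, removes the form.** Progression-free: 0.5^(5.52/5.6) = 0.505.

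- OS 9: 0.654 − 0.505 = 0.149; 0.149/0.654 = 23% of the living, about 9 of 63
- OS 15: 0.775 − 0.505 = 0.270; 0.270/0.775 = 35% of the living, about 17 of 63

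**Reading B: progression found at the week-24 scan still leaves that visit's form in place.** The scan and the form are in the same list, so the effective cut-off is nearer the week-16 scan. Progression-free then: 0.5^(3.68/5.6) = 0.634.

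- OS 9: 0.654 − 0.634 = 0.020; 0.020/0.654 = 3% of the living, about 1 of 63
- OS 15: 0.775 − 0.634 = 0.141; 0.141/0.775 = 18% of the living, about 9 of 63

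These two are minimum values. Some patients progression-free at week 16 die before week 24, and progression detected between scans adds to the number not asked.

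**Favourable PFS, reading A.** With median PFS 11 and OS 15: 0.5^(5.52/11) = 0.706; 0.775 − 0.706 = 0.069; 0.069/0.775 = 9% of the living, about 4 of 63.

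**Bias in the mean change.** Bias = share of living patients not asked × difference in mean change between those asked and those not asked. The difference is unknown. At an assumed 10 points worse, shares of 3% to 35% give 0.3 to 3.5 points; the favourable case gives 0.9. None of these figures includes patients off drug without progression who may not be asked under 8.2 f).

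**Week 8.** That form belongs to the fixed first-assessment visit, so progression found at that scan need not remove it. The problem lies mainly with the later form.

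**The case against.** The strongest reply is that stopping at progression is a coherent design choice. Survival-only follow-up after progression is a trial-wide rule, and Table 11's post-progression column contains only survival and new therapy. Section 8.2 c) simply applies it. That is fair as far as collection goes, but section 10.2 then needs to say that quality of life is measured while progression-free, and it does not.

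Several stronger readings are tempting but go beyond the text:

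- *Sections 8.1 and 8.2 flatly contradict each other.* Section 8.1 sets no condition, but it does not say that every patient is asked whatever their status. The two schedules are unreconciled.
- *A week-24 endpoint is biased by a known amount.* Section 10.2 names no time point and the SAP tabulates w8 and w16, so no planned table yet carries a week-24 mean. This mismatch needs its own repair, and correcting the row label cannot recover forms never requested.
- *Patients who stop for toxicity are not asked at week 24.* The sentence in 8.2 f) follows the 12-month clause and may apply only after it. The Modified Barthel Index, which is scheduled in follow-up before progression, gives it a form to govern. Against that, no QLQ-C30 is scheduled after week 24. The wording is ambiguous and sites could differ.
- *Only patients doing well are measured.* Stable disease counts as progression-free, and patients off drug may still be asked.
- *Quality of life on the regimen is overstated.* Most patients stop the drugs at progression, so their later scores are largely off the regimen. Section 5.3 does allow some to continue after progression.

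The 5.6-month PFS comes from a trial that did not allow local therapy after the drugs, so it may be pessimistic here. That supports giving a range.

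**Conclusion.** The point holds in a limited form. The definition in section 10.2 and the schedule in 8.1 are unrestricted. Collection under 8.2 c) stops at progression, 8.2 f) is unclear for patients off drug without progression, and the analysis uses observed data only. The later result will describe mainly progression-free patients and, as written, would be presented as the cohort's.

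The share of living patients not asked is roughly 3% to 35%, depending on whether progression at the week-24 scan cancels that form and on the assumed OS. It is about 9% with the longer cited PFS and 15-month OS. A reader might take 23% to 35% as the estimate, but the documents do not settle which reading applies. The bias of 0.3 to 3.5 points rests further on an assumed 10-point difference. Severity is minor to moderate: the endpoint is secondary and descriptive, and the primary response analysis is unaffected.

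**What to change.** **Main change**

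- In section 10.2 and the SAP, restate the endpoint as change from baseline in global health status while progression-free, and name its time points.
- Align the SAP's w16 rows with the scheduled week 24.
- At each time point, report forms received over patients alive, and the number alive but not asked because of progression or stopping drug.
- In 8.2 c) item 4 and 8.2 f), state that patients off drug without progression still complete the scheduled week-8 and week-24 forms.

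The cost is wording and one extra line per table. SAP section 3.5 already refers to database closure, so forms not collected may no longer be obtainable. Restating the endpoint and reporting the counts remain possible.

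**Alternative, if the sponsor wants quality of life regardless of progression.** The form must be requested from living patients after progression. This also means amending the survival-only rule in section 5.3 and the synopsis, and the date-of-death-only rule after a treatment switch in 8.2 f). The survival contact in 8.1 ("It is recommended to maintain contacts by phone or by other methods every 4 weeks") could carry the request. It is only a recommendation, however, and survival status may come from family or a physician, who cannot complete a patient's questionnaire. The cost is added patient burden and incomplete return.
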